Document Cover Page

Full Analysis Plan

Study Title:

Enhancing COVID-19 Vaccination Intentions by Eliciting Prosocial Altruistic Motives:
Evaluating the Efficacy of a Brief Video-Based Intervention

NCT number: NCT04960228

Date of Document: February 5th, 2022

Analysis Plan

Sociodemographics

For baseline sociodemographics we calculated proportions, means (and standard deviation, SD) and used the Pearson Chi-Squared Test and the Welch two sample t-test to evaluate if the two study groups differed significantly.

Objectives 1 and 2.

At baseline and post-intervention and for each of the study groups we calculated the proportion of participants in each of the four PAPM intention stage i.e., *unengaged*, *undecided*, *decided not*, and *decided to*. For each study group we calculated the pre-to post transitions in intentions to receive the COVID-19 vaccine. To estimate the pre-to-post intervention change in vaccine intentions we used a binary outcome (i.e., Vaccine intenders corresponding to the stage *decided to*; and Vaccine non-intenders that included stages *unengaged*, *undecided*, and *decided not*) and the McNemar's Chi-squared test. Post intervention, we estimated the between group difference in vaccine intentions using the four-stage PAPM outcome and the Pearson Chi-Squared Test.

Exploratory Analyses with PAPM stages

To estimate pre to post changes in PAPM intention stages we conducted exact tests of symmetry (4x4 contingency tables) that comprise pairwise McNemar tests (using the “nominalSymmetryTest” function available in the R package “rcompanion”) (1). For each study group we used the significant transitions between vaccine intention stage pairs for calculating the total number of participants that changed towards increased vaccination intentions (e.g., from *undecided* to *decided to*) and estimated the between-group difference using the Chi-squared two-sample test for equality of proportions.

All statistical analyses were conducted using the R software v. 4.0.5.(2).

References

1. Mangiafico S. Package 'rcompanion' 2022 [Available from: <https://cran.r-project.org/web/packages/rcompanion/rcompanion.pdf>].
2. R Development Core Team. R: A Language and Environment for Statistical Computing. R Foundation for Statistical Computing Vienna, Austria 2005 [Available from: <http://www.R-project.org/>].

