
Study Rationale

To the best of our knowledge, there have been no studies that examined the impact of altruism on COVID-19 vaccine intentions using a video-based intervention.

Purpose of the Research

This study has two objectives: 1) To develop a video-based intervention designed to elicit altruism in increasing younger adults' intentions to receive a COVID-19 vaccine 2) To estimate the efficacy of this video intervention on young Canadians' (ages 20-39) intentions to receive a COVID-19 vaccine. The results of this study will be used by public health authorities to increase COVID-19 vaccine uptake.

Development and validation of the video-based intervention

Our team will work with a media company (Akufen) who will be contracted by us to create a two-minute video designed specifically to elicit altruistic motives to influence COVID-19 vaccine intentions and uptake in our target population. The draft contract with the company Akufen is attached in section 13 “Other document” on Nagano (F11P-20611) and has also been sent to the LDI contracts office for approval (ID# RCO-3977) on 15 February 2021.

As part of the development of our video, a preliminary aim will be to ensure clarity and face validity of our intervention with our target audience of Canadians between 20 and 39 years old.

Methods

Sample

We will conduct two focus groups with a convenience sample of 6-8 participants to obtain feedback regarding comprehension and content of the video. Inclusion criteria are being 20 to 39 years of age, being current Canadian residents, and speaking English or French. Our only exclusion criterion is having received any number of doses of any of the COVID-19 vaccines. We will recruit a diverse sample of participants, with both males and females, anglophones and francophones, and with a range in educational level.

Recruitment Strategy

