While we have essentially kept the pre-post evaluation format as per the approved MI4 proposal we have decided to improve the research design by adding a control condition, therefore making this a randomized controlled trial. The full research proposal that has been submitted to the McGill Interdisciplinary Initiative in Infection and Immunity (MI4) and approved for funding is attached in section 13 "Other document" on Nagano (F11P-20611).

Methods

Sample

A survey will be administered online to a sample of Canadian residents aged 20-39 years old in both English and French. Our only exclusion criterion is having received any number of doses of any currently available COVID-19 vaccine. A sample of 2,630 participants will be drawn from a database panel provided by Dynata, the world's largest first-party data and insight

platform, to complete the survey. Dynata's use of Canadian census data from Statistics Canada and quota-based sampling will ensure that the sample will closely match the Canadian population in terms of sex, first language English/French, population density (i.e. urban vs. rural), and household income.

To calculate the required sample size for the within-participant change in vaccine hesitancy (i.e., pre-post intervention) we used the latest survey data showing that approximately 40% of Canadians in this age group are COVID-19 vaccine hesitant i.e., don't know yet or would refuse vaccination. Estimating a 5% decrease of hesitancy in the intervention group and a correlation of about 0.45 between paired observations, the intervention group requires a sample size of 1315 pairs for detecting a 5% change of marginal proportions at a power of 80% and two-sided significance of 5%.

We will use 1:1 randomization of participants. Thus, 50% will be allocated to the intervention and 50% to the control group. Using equal size groups will allow us to detect a between group difference in vaccine intentions of 5-6% with a power of 0.8 and a two-sided significance of 5%. The total sample required for this study is 2630 participants i.e., 1315 in the intervention group and 1315 in the control group.

Recruitment Strategy

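### No test is named as the one that decides efficacy, and the binary intender outcome is tested only pre-to-post within arms, never between the randomised arms

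*SAP*

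**What the plan says.** The second aim in the Protocol's Purpose of the Research is "To estimate the efficacy of this video intervention on young Canadians" and their intentions to be vaccinated. Its Study design section describes "adding a control condition, therefore making this a randomized controlled trial". The Sample section of the efficacy study begins its sizing "To calculate the required sample size for the within-participant change in vaccine hesitancy", and then says that equal groups can "detect a between group difference in vaccine intentions of 5-6% with a power of 0.8".

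Under Objectives 1 and 2, the SAP first reports descriptively: "we calculated the proportion of participants in each of the four PAPM intention stage". Two tests follow.

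- Within arm: "To estimate the pre-to-post intervention change in vaccine intentions we used a binary outcome". Intenders are those who *decided to*, non-intenders are the other three stages, and the test is McNemar's.
- Between arms: "Post intervention, we estimated the between group difference in vaccine intentions using the four-stage PAPM outcome and the Pearson Chi-Squared Test".

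The remaining between-arm test of intentions is in the exploratory section. It counts people who moved towards vaccination, and begins: "For each study group we used the significant transitions between vaccine intention stage pairs". Neither document calls any endpoint or test primary.

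**The concern.** Two tests share one heading, they answer different questions, and nothing ranks them.

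The McNemar test matches the main sizing argument but leaves the control arm out. It cannot separate an effect of the video from change that both arms share, for example from being asked the same question twice in one survey, or from reading any COVID-19 content.

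The four-stage Pearson test is a valid randomised comparison. But it is non-directional on 3 degrees of freedom, and it ignores both the baseline stage and the factors used to stratify the randomisation. It can be significant when the share who *decided to* is the same in both arms.

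The per-stage proportions would show the sign and size of the difference in *decided to*, but no test or interval is planned for that difference. The Protocol says the results will inform public health authorities, and this is the figure they would most naturally use. Change is compared between arms only in the exploratory section, and only over transitions already found significant.

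**Working it through.** **Inputs from the Protocol (Sample):** n = 1315 per arm, 40% hesitant, a 5-point fall to 35%, correlation 0.45 between paired answers, two-sided 5%. **Assumed, because the documents do not give them:** the split across the four stages, any drift shared by both arms, and that the 0.45 carries over to baseline adjustment.

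**1. The Protocol's between-group figure.** For two proportions:

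- pooled SE = √(2 × 0.375 × 0.625 / 1315) = 0.01888
- unpooled SE = √((0.40 × 0.60 + 0.35 × 0.65) / 1315) = 0.01886
- power = Φ((0.05 − 1.96 × 0.01888) / 0.01886) = 75.5%

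Solving for 80% power gives 5.28 points. The stated 5-6% therefore reproduces, as a binary comparison. A single percentage difference would not fix the power of a four-stage test, as step 3 shows.

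**2. Within-arm McNemar when both arms drift equally by s.** With p₁ = 0.40 and p₂ = 0.40 − s:

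- p₁₁ = p₁p₂ + 0.45√(p₁q₁p₂q₂)
- discordant share D = p₁ + p₂ − 2p₁₁
- P(significant) ≈ Φ((s√n − 1.96√D) / √(D − s²)), plus the opposite tail, which matters only for small s

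At s = 0.02, D = 0.262 and the result is 29%.

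| Shared drift (points) | Video-arm McNemar significant | Between-arm binary test significant |
|---|---|---|
| 0 | 5% | 5% |
| 0.5 | 6% | 5% |
| 1 | 11% | 5% |
| 2 | 29% | 5% |
| 3 | 57% | 5% |

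Simulation with 200,000 trials agrees. These are not errors of the McNemar test, which correctly detects change over time. They show how often its answer would differ from the between-arm truth.

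**3. Four-stage Pearson test, true 5-point gain in *decided to* from 60%.** Noncentrality λ = n Σ (difference)² / (sum of the two arms' proportions), 3 df.

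- Movers leave the other three stages in proportion: λ = 7.01, power 59%.
- Movers all leave one stage that holds 20%: λ = 1315 × (0.0025/1.25 + 0.0025/0.35) = 12.0, power 84%.
- That one stage holds 35, 30, 25, 15, 13.3 or 10%: power 63, 69, 76, 93, 96 or 99%.

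The binary test has 75% throughout, so the four-stage test may be weaker or stronger.

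**4. Four-stage Pearson test, no difference in *decided to*.** Points move from *decided not* to *undecided*. Splits are given as *decided to* / *unengaged* / *undecided* / *decided not*.

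| Points moved | 60/10/20/10 | 60/5/20/15 |
|---|---|---|
| 1 | 12% | 10% |
| 2 | 37% | 29% |
| 3 | 75% | 60% |
| 4 | 96% | 87% |

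For 3 points in the first split, λ = 1315 × (0.0009/0.43 + 0.0009/0.17) = 9.71. A 60/4/18/18 split gives 83% at 4 points. A binary test of *decided to* stays at 5% in every cell.

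**5. Between-arm binary test adjusted for baseline.** The variance shrinks by about 1 − 0.45² = 0.7975, so SE = 0.01886 × √0.7975 = 0.01684 and power = Φ(0.05/0.01684 − 1.96) = 84%. For correlations from 0.30 to 0.80, power runs from 79% to 99%. The detectable difference at 80% power is 4.7 points at 0.45. The 95% CI half-width is about 3.3 points adjusted and 3.7 unadjusted.

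**The case against.** - **The SAP may have one test per objective.** The Protocol's first objective is developing the video, which neither test addresses. The SAP's two objectives could therefore be pre-to-post change and between-group difference, and Pearson would be the efficacy test by default. This is a possible reading, but the SAP does not state it. Even so, the efficacy test would be non-directional and would match neither the binary outcome nor the sizing.
- **The documents never say that a McNemar result will be read as efficacy, and a survey of about 10 minutes leaves little room for calendar drift.** Both points stand. Repeat-question effects and effects of the control text remain possible, but the documents give no size for them, so step 2 is a range and not a forecast.
- **Movement from *decided not* to *undecided* is a real change in the four-stage outcome.** It is, and rejecting there is not an error. It still does not show that more people decided to be vaccinated.
- **The percentages in step 4 depend on the split.** They do, and moving 4 points out of a 10% stage is a large shift. The pattern holds in each split tried.
- **A reader could derive the difference and its interval from the reported proportions, and an unadjusted difference with a CI would close most of the gap.** This is largely right. Adjustment is for precision, not validity. But a result that must be reconstructed by the reader is not a planned analysis.

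**Conclusion.** The concern holds. No test is designated to decide efficacy, and the binary intender outcome has no planned between-arm test or interval. These two facts rest on the text alone.

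The sizes rest on assumed drift, assumed stage splits and the Protocol's 0.45 correlation. Equal drift of 1 to 3 points would make the video-arm McNemar test significant 11 to 57% of the time. Under the two tabulated splits, the four-stage test would reject 60 to 75% of the time for a 3-point shift that leaves *decided to* unchanged. Lower power for the four-stage test is possible but not established (59 to 99%, against 75% for the binary test).

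A valid randomised test is planned, so the trial is not invalidated. This should be corrected because the answer to its main question is left undefined.

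**What to change.** Name one primary efficacy analysis: the between-arm risk difference in post-intervention *decided to*, with a 95% CI, at two-sided 5%. Estimate it by logistic regression on arm, baseline PAPM stage, first language, sex, population density and household income, standardised to a risk difference. If the model does not converge because few people change stage, use a linear model with robust standard errors. Report the unadjusted difference alongside. Keep the four-stage Pearson test as secondary and label the per-arm McNemar tests descriptive. Restate the between-group sizing: for 40% against 35%, about 75% power unadjusted and 84% adjusted, with 80% power at about 5.3 and 4.7 points respectively.

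The cost is wording in both documents and one analysis of data already collected. The SAP is dated February 2022 and written in the past tense. If results were known, the choice must be disclosed as post hoc, and its value is then clearer reporting, not pre-specification.

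The within-arm test has about 95% power when recalculated at 1315 pairs, although the Protocol states 80%; against the recalculated figure, headline power falls. If the video arm moves 5 points and controls move 1 or 2 (assumed), adjusted power is about 66% or 43%.

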Dynata will send invitations in various forms (e.g., e-mail invitations, text messages and in-app alerts) to recruit eligible participants from their existing panel (individuals who have signed with Dynata and have expressed willingness to receive invitations to various appropriate surveys) until recruitment goals and quotas are met. For recruitment purposes only, Dynata collects IP addresses as an identifier to make sure that the same person is not recruited for the same study multiple times. IP addresses are not retained by Dynata after the study and are not shared with the researchers. Dynata has identifying socio-demographic information that allows them to use our inclusion and exclusion criteria to recruit eligible participants. None of this information is communicated to the research team. Please refer to the "confidentiality" section for Dynata's privacy policies.

An electronic consent form describing the study goals and procedure will be provided at the start of the survey, after which participants will be asked whether they consent to taking part in the survey. Once they click on the icon that states they agree to participate, consent will be implied. The information collected for the survey is completely anonymous. If they decline, the survey will be terminated.

Procedure

Stratified randomization will be used to allocate participants to either: 1) intervention condition: viewing a 2-minute altruism-eliciting video, or 2) control condition: reading a text containing information (from the Public Health Agency of Canada website: <https://www.canada.ca/en/public-health/services/diseases/2019-novel-coronavirus-infection/prevention-risks.html>) about general health behaviours and public health recommendations concerning COVID-19 e.g. hand hygiene and respiratory etiquette, wearing non-medical masks, physical distancing, etc. Within each stratum (first language, sex, population density and household income), participants will be allocated randomly using a 1-to-1 ratio (1 to the intervention condition and 1 to the control condition).

The online survey will be approximately 10 minutes in length and will be available in both French and English. After reading the introductory statement of the study, participants will

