be asked whether they consent to taking part in the survey. Those who consent to taking part in the survey will be invited to go to the next page and start completing the survey. Participants will first be asked to answer several socio-demographic questions and will be asked to choose one of the following categories which describe their COVID-19 vaccine decision-making stage according to the Precaution Adoption Process Model (PAPM): unengaged, undecided, decided not to receive the vaccine, or decided to receive the vaccine.

Subsequently, depending on their randomly assigned condition, participants will either be shown a 2-minute altruism-eliciting video, or a brief informational text. After viewing this content, to ensure that participants paid attention, participants will answer questions about the contents to check their understanding.

Finally, participants will: 1) once again be asked to choose their COVID-19 vaccine decision-making stage; 2) be asked questions regarding previous vaccination history (e.g. seasonal influenza), lifestyle factors, self-perceived health status, personal history of SARS-CoV-2 infection, and preferred health-information channels; and 3) complete validated scales regarding altruism, empathy, personal distress, and vaccine hesitancy.

Funding

This study is funded by the McGill Interdisciplinary Initiative in Infection and Immunity (MI4) (<https://www.mcgill.ca/mi4/>). Neither the principal investigator nor the institution is in a situation of conflict of interest as a result of this funding.

Risks and Concerns

Participating in this research study has no known or serious risks. There is no evidence in the scientific literature that eliciting altruism could produce negative consequences or emotions in participants. However, it is possible that participants of the focus group may experience discomfort or upset as the result of the research intervention.

In the event that participants experience discomfort after the study procedures, they will also be provided with the link to a governmental website where they will find available resources in their regions: <https://www.canada.ca/en/public-health/services/mental-health-services/mental-health-get-help.html>.

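### The only between-group test for Objectives 1 and 2 leaves out baseline PAPM stage and the stratification factors: it is valid, but gives up precision that the trial's own data could supply.

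*SAP*

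**What the plan says.** The SAP's paragraph on Objectives 1 and 2 has two inferential parts. Within each arm, "To estimate the pre-to-post intervention change in vaccine intentions we used a binary outcome" (intender versus non-intender) with McNemar's test. Between arms, "Post intervention, we estimated the between group difference in vaccine intentions using the four-stage PAPM outcome and the Pearson Chi-Squared Test". The second is a 2×4 table with 3 degrees of freedom. No covariate, no stratified analysis and no confidence interval for a between-group difference is named.

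The SAP's exploratory section also compares the arms on the number who moved towards vaccination, but that number is built selectively: "For each study group we used the significant transitions between vaccine intention stage pairs".

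The protocol (efficacy part, Procedure) has participants "choose one of the following categories which describe their COVID-19 vaccine decision-making stage" before the video or text and again afterwards, in one survey of about 10 minutes. On allocation it says: "Within each stratum (first language, sex, population density and household income), participants will be allocated randomly using a 1-to-1 ratio". Under Sample it assumes "a correlation of about 0.45 between paired observations", states that "the intervention group requires a sample size of 1315 pairs", and says that equal groups can "detect a between group difference in vaccine intentions of 5-6% with a power of 0.8".

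**The concern.** The same item is answered twice within minutes, so the baseline answer may well be the strongest predictor of the post-intervention answer. A between-group comparison of post values alone treats that predictable variation as noise. The strata are likewise used to balance the arms and then dropped from the analysis.

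Neither omission biases the comparison. Randomisation protects the chi-square, and ignoring stratification makes it, if anything, conservative. What is at stake is the precision of the randomised estimate, which is the reason for having a control arm.

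The SAP's other uses of baseline do not fill the gap. The McNemar and symmetry tests are within-arm and do not use the control group. The exploratory comparison does use change from baseline, but only the transitions found significant in each arm count towards it. What is counted therefore depends on the results and may differ between arms.

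**Working it through.** **Inputs.** From the protocol's Sample section: 1315 per arm, 40% hesitant, a 5-point fall, correlation about 0.45, two-sided 5%, power 80%. Hesitant is treated as the SAP's non-intender category. The correlations 0.6 and 0.8, the control-arm correlations and the split of non-intenders over stages are assumptions.

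**1. The protocol's between-group figure.** Power = Φ[(d − 1.96·SE₀)/SE₁].
- SE₀ = √(2 × 0.375 × 0.625/1315) = 0.01888.
- SE₁ = √((0.40 × 0.60 + 0.35 × 0.65)/1315) = 0.01886.
- At d = 0.05: (0.05 − 0.0370)/0.01886 = 0.69, so power is 75.5%. At 5.5 points it is 83%, and at 6 points 89%.
- Power reaches 80% at 5.3 points, so the stated 5-6% reproduces.
- 95% CI half-width: 1.96 × 0.01886 = 3.7 points.

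**2. Effect of adjusting for baseline.** Linear adjustment multiplies the variance of the risk difference by 1 − ρ². At 0.45 this is 1 − 0.2025 = 0.7975: variance about 20% lower, SE × 0.893 (about 11% lower), equivalent to 1315/0.7975 = 1649 per arm unadjusted.

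| ρ, both arms | Variance factor | Power at 5 points | 80% detectable difference |
|---|---|---|---|
| unadjusted | 1 | 75.5% | 5.3 points |
| 0.11 | 0.988 | 76.0% | 5.25 points |
| 0.45 | 0.798 | 84.3% | 4.7 points |
| 0.6 | 0.64 | 91% | 4.2 points |
| 0.8 | 0.36 | 99% | 3.2 points |

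At 0.45 the CI half-width becomes 3.7 × 0.893 = 3.3 points.

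Simulation (20,000 trials per setting, standardising over baseline intender status) gave variance ratios of 0.987, 0.802, 0.639 and 0.365 for the four correlations. At 0.45, simulated power was 84.4% adjusted against 75.8% unadjusted. Null rejection of the adjusted analysis was 4.7% to 5.4%.

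**3. Unequal correlations.** The protocol gives no control-arm value. With a common slope the factor is close to 1 minus the square of the mean correlation:
- Control 0.45, intervention 0.11: 1 − 0.28² = 0.922, a gain of about 8% (simulated power 79%).
- Control 0.8, intervention 0.45: 1 − 0.625² = 0.609, a gain of about 39% (simulated power 93%).

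**4. Why 0.45 cannot be taken as settled.** McNemar pairs: n = [1.96√ψ + 0.8416√(ψ − d²)]²/d². At correlation 0.45 the discordant cells are 0.155 and 0.105, so ψ = 0.260 and n = 813, not 1315. Solving for 1315 pairs gives a correlation of about 0.11. The protocol's two figures therefore point to different gains: 20% and about 1%.

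**5. The planned 3-df test.** Its noncentrality is 1315 × Σ(aⱼ − bⱼ)²/(aⱼ + bⱼ) over the four stages. Take 60% versus 65% intenders.
- Shift spread proportionally over the three non-intender stages: 1315 × (0.0025/1.25 + 0.0025/0.75) = 7.01, power 59%.
- Shift only from *undecided*, with share u: 1315 × (0.0025/1.25 + 0.0025/(2u − 0.05)). For u = 25%, 20% and 15%, power is 76%, 84% and 93%.

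Steps 2 and 3 concern the binary risk difference and do not carry over to this test. The documents give nothing from which to size the gain from the strata.

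**The case against.** The strongest reply is that nothing here is an error. An unadjusted test after 1:1 randomisation is a legitimate choice, neither document promises an adjusted one, and on the binary calculation the 5-6% target is met. All of that stands, and it makes this an efficiency recommendation.

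Second, the 20% belongs to a binary comparison that the SAP does not plan between arms, and it comes from baseline intender status alone, not from the strata. This also stands. Moving from four stages to a binary outcome may matter as much as adjustment: under a proportional shift the four-stage test has 59% power at 5 points, against 75.5% for the unadjusted binary test. The two changes must be shown separately.

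Third, the gain ranges from about 1% to 64%. True, but 0.45 is the only correlation the protocol states; 0.11 appears only by solving back from 1315 pairs.

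Fourth, the strata may not be in hand. The protocol mentions socio-demographic survey questions without naming the four factors, and says that the survey company does not pass on its own identifying socio-demographic information. Baseline PAPM stage is certainly held; the stratum codes may have to be requested.

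Fifth, the SAP is dated February 2022 and written in the past tense, so an added model could be chosen after seeing results. Labelling answers this only in part.

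**Conclusion.** The point holds as an improvement, not a correction. The SAP's only between-group test for Objectives 1 and 2 omits baseline stage and strata, and no other planned analysis supplies a baseline-adjusted randomised estimate.

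The gain of about 20% in variance is conditional: binary outcome, correlation 0.45 in both arms, 40% versus 35%, and all 1315 per arm analysed. It is not a floor. No validity problem follows, and the statement that the 5-6% target is met applies to the binary calculation, not to the four-stage test. Confidence in the size of the gain is moderate, because the protocol's correlation and its number of pairs disagree.

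**What to change.** - Add a between-group risk difference in vaccine intenders, the SAP's own binary outcome and the scale of the protocol's target. Fit a logistic or linear-probability model with arm, baseline PAPM stage and the four stratification factors, fixing the model form and the coding of income in the SAP text. Report a standardised risk difference with a robust 95% CI. An adjusted log odds ratio is not a substitute: it targets a conditional effect, and its SE need not shrink.
- Report the unadjusted risk difference and keep the four-stage chi-square alongside, so that the change of outcome and the adjustment can be told apart.
- If results had already been seen, label the adjusted analysis as added later; it does not replace the main test.
- State which pre-post correlation underlies the 1315 pairs.

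The cost is one regression and a few lines of SAP wording. No new participant data are needed for the baseline adjustment. For the strata, the survey company should supply the codes used for allocation, in anonymised form, if they differ from the survey answers.

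### The exploratory between-arm count of increased intention keeps only transitions significant within each arm, which can push its false-positive rate far above 5%

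*SAP*

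**What the plan says.** The SAP section headed "Exploratory Analyses with PAPM stages" has three steps.

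1. Within each arm, pre-to-post change is examined by "exact tests of symmetry (4x4 contingency tables) that comprise pairwise McNemar tests". Four stages give six stage pairs per arm.
2. The results decide what is counted: "For each study group we used the significant transitions between vaccine intention stage pairs for calculating the total number of participants" who moved towards greater intention.
3. For these totals the SAP "estimated the between-group difference using the Chi-squared two-sample test for equality of proportions".

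The SAP has no rule for a stage pair that is significant in one arm but not in the other. For this step it also does not state the denominator, the full ordering of the four stages (one example of an upward move is given), the significance threshold, or whether the six pairwise p-values are adjusted.

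The other between-arm test, under Objectives 1 and 2, has no selection step: "Post intervention, we estimated the between group difference in vaccine intentions using the four-stage PAPM outcome".

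**The concern.** The symmetry tests are pre-to-post tests run within an arm, so the transitions found significant for each study group are most naturally that arm's own. A difference in statistical significance between the arms is then turned into a difference in the outcome itself. Two arms that behave alike can fall on either side of the 5% threshold by chance, and the arm that falls short has its movers scored as zero.

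The selection and the count also measure different things. McNemar's test looks at net asymmetry (up minus down), while the count takes all upward movers in the pair. A pair with much movement in both directions and a borderline net shift can therefore remove a large number of people from one total.

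This is the only test in the SAP that compares pre-to-post movement between the arms, and the protocol (Purpose of the Research) expects public health authorities to use the results. What is at stake is a reported benefit of the video that could come from the counting rule alone.

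**Working it through.** **Inputs from the documents.** Protocol, Sample section of the efficacy evaluation: "We will use 1:1 randomization of participants", with "1315 in the intervention group and 1315 in the control group"; two-sided 5%; about 40% hesitant at baseline, so 0.40 × 1315 = 526 non-intenders per arm. The planning assumption is: "Estimating a 5% decrease of hesitancy in the intervention group and a correlation of about 0.45 between paired observations". **Assumed, because not in the documents:** the split of the 40% over three stages, all four-stage transition rates, and raw versus FDR-adjusted (Benjamini-Hochberg) pairwise p-values. Both versions were run.

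**The plan's own figure.** No error rate or power is stated for this analysis. The nearest figure is the detectable between-group difference of 5-6 points. With 1315 per arm and 40% as reference, power is 0.755 for 5 points and 0.890 for 6, and 80% power falls at 5.28 points, so it reproduces. It does not bear on the selection step.

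**Smallest count that can be selected.** The exact two-sided McNemar p-value for u up and 0 down is 2 × 0.5^u. For u = 5 it is 0.0625 and for u = 6 it is 0.031, so a selected upward pair has at least 6 upward movers.

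**That count against zero.** The continuity-corrected statistic is N(|ad − bc| − N/2)² / (product of the four margins). For 6/1315 against 0/1315:

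2630 × (6 × 1315 − 1315)² / (6 × 2624 × 1315²) = 4.18, p = 0.041.

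With 526 per arm, p is also 0.041. Larger counts against zero give smaller p-values. With equal arms, therefore, whenever one arm has a selected upward pair and the other has none, the between-arm test rejects. FDR adjustment only raises the count needed for selection, so this still holds.

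**Example.** One arm has 30 up/15 down (p = 0.036) and the other 28 up/15 down (p = 0.066). Compared directly, 30 against 28 is 2/1315 = 0.15 points, p = 0.89. Under the SAP's rule it becomes 30 against 0: 30/1315 = 2.3 points, chi-squared 28.4, p = 1e-7.

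**One drifting pair.** If only one pair can be selected, and is selected with probability q in each arm, the arms disagree with probability 2q(1 − q), and each disagreement is a rejection. This gives 50% at q = 0.5, 32% at q = 0.8 and 9.5% at q = 0.95.

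**Simulation, identical arms.** 10,000 trials per scenario, 1315 per arm, the same transition table in both arms. Baseline *decided not*/*unengaged*/*undecided*/*decided to* was 15/5/20/60%, ordered as listed; a 10/10/20/60% split changed results by about 1 point. Pairs with exact McNemar p < 0.05 and up > down were selected within each arm, their upward cells summed, and the totals compared by continuity-corrected chi-squared. Expected up/down counts per arm are in the order *undecided*–*decided to*, *decided not*–*decided to*, *unengaged*–*decided to*, *unengaged*–*undecided*, *decided not*–*undecided*.

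| Scenario (net gain in intenders) | Expected up/down per arm | Raw | FDR |
|---|---|---|---|
| Almost no movement (+0.1) | 6/5, 1/1, 1/1, 3/2, 3/3 | 9% | 1% |
| Movement, no net drift (0) | 25/25, 4/4, 6/6, 12/12, 12/12 | 13% | 2% |
| One pair drifts (+1.1) | 30/15, 2/2, 2/2, 6/6, 9/9 | 51% | 42% |
| Weak drift (+0.8) | 20/12, 3/2, 4/2, 10/6, 12/8 | 54% | 25% |
| Moderate drift (+1.7) | 30/15, 5/2, 6/2, 15/6, 18/9 | 61% | 65% |
| Stronger drift (+3.2) | 45/15, 8/2, 8/2, 18/6, 22/9 | 38% | 47% |
| Net +5.0, correlation 0.45, both arms | 130/88, 50/34, 24/16, 15/8, 25/17 | 66% | 71% |
| Very strong drift (+9.0) | 90/10, 20/1, 20/1, 35/3, 50/5 | 5% | 5% |

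Counting only moves into *decided to*, which needs no stage ordering, the five scenarios from one drifting pair to net +5.0 give 17-64% raw and 18-67% FDR. Selecting pairs only after a significant overall symmetry test lowers the first two scenarios to 3-4% raw, but leaves those five at 38-68% raw and 24-71% FDR.

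**Effect on the estimate.** Moving from 40% to 35% with correlation 0.45, the proportion hesitant both times is 0.40 × 0.35 + 0.45 × √(0.40 × 0.60 × 0.35 × 0.65) = 0.245. So 15.5% move up and 10.5% move down. With these rates in the intervention arm and a symmetric 10.5% each way in control, the true difference in upward movers is 5.0 points. The rule reports 14.4 points on average (12.7 with FDR), because control's upward movers are usually scored as zero.

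**Alternatives on the same eight scenarios and both splits.** Pairs significant in either arm, counted in both: 0.3-6.3%. All upward moves: 3.0-4.5%. Non-intender to *decided to*: 2.5-4.2%. Moves away from *decided to*: 2.7-4.2%. Net movement scored −1/0/+1: 4.7-5.7%.

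**The case against.** - **The sentence is ambiguous.** The reference to each study group could govern the counting, with one common list of transitions. The error rate then stays at or near 5%. This is possible, but the SAP does not say it, and the tests that define significance are within-arm tests. At the least, a rule for discordant pairs is missing.
- **The 66%/71% figure does not follow from the planning values alone.** The protocol plans the 5-point fall for the intervention arm only; giving it to control as well is an assumption, and the four-stage split matters. If one pair carries all the movement, the same net change and correlation give 14% raw and 32% FDR. This stands, and the planning values support a range of 14-66% raw and 32-71% FDR.
- **With no net drift in either arm the inflation is modest or absent.** Correct: 9-13% raw and 1-2% FDR. Large inflation needs some drift in the control arm too, and the documents give no expected value for that.
- **Certain rejection needs near-equal arms.** Correct. Six movers in an arm of 1340 against none in 1290 gives p = 0.046; in 1365 against 1265 it gives p = 0.051.
- **The unstated denominator matters little.** Also correct: using baseline non-intenders changes the rates by about 2 points.
- **The analysis is exploratory.** That limits the consequence, but does not make the rule sound.

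**Conclusion.** The concern holds. As written, the rule can declare a difference between arms that behave identically and can greatly overstate a real one. With 1315 per arm, the minimum-count result (6 against 0, p = 0.041) needs no assumed transition rates. How often the error occurs does depend on them: from 1-13% with little or no net drift, up to 71% with small to moderate drift in both arms, and back to 5% when drift is very strong. These rates rest on assumed stage splits and transition rates, and on reading the selection as arm-specific.

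The damage is confined to this one exploratory comparison. The within-arm McNemar tests and the post-intervention four-stage comparison for Objectives 1 and 2 stand as they are. The rule should be corrected before the exploratory result is interpreted.

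**What to change.** Define one outcome, the same in both arms and independent of any significance test, over a stated denominator.

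- **Simplest choice:** the proportion of baseline non-intenders who move to *decided to*, compared by a risk difference with 95% CI. No ranking of the other three stages is needed.
- **If movement among the lower stages is of interest:** count all upward moves in both arms and state the stage ordering.
- **Opposite direction:** report moves away from *decided to*, among baseline intenders, as a separate proportion in the same way.
- **If net movement is compared:** score it −1/0/+1 and use the variance of a difference in means.
- **Pairwise McNemar tests:** keep them as description, not as a filter, and state whether their p-values are adjusted.

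If one common list of transitions was intended, saying so would remove most of the inflation, but the list would still be chosen from the data; a fixed outcome avoids that.

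The cost is a change in SAP wording and a re-tabulation of the existing 4x4 tables, with no new data. The SAP is dated February 2022 and written in the past tense, so the re-tabulation should be labelled post hoc if the data have already been seen.
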